- Research will be conducted during [name] clinical time. [name], a UCF Health board-certified physician, will perform the screening of eligible participants. [name] has significant prior experience conducting research, knowledge of the regulations and customs at UCF Health, and works regularly with patients performing laser treatments. Off-label laser treatments currently performed are fractionated CO2 laser for morphea, 1064nm and 532nm laser for sarcoidosis and acne, and 532nm laser for cutaneous lupus among others. Experience has been presented at invited talks/grand rounds. All treatments will be administered by [name].
- All individuals assisting in the research study will be provided a copy of the approved IRB study protocol and given the opportunity to meet with the principal investigator before recruitment begins. The principal investigator, [name], will be responsible for informing all research staff of their research-related duties during a personal meeting or via phone or email. The contact information of the principal investigator and co-principal investigators will be distributed to all research staff and the participants.

- The study will be conducted at the UCF Health Clinic, see section 5 (Setting of the Human Research). Extramural funding will be sought from various organizations or industry.
- The chances of a research related injury are extremely rare. However treatment for research related minor injuries will be made available at no cost by [name] if possible. For injuries that cannot be treated by [name] the participant will be referred elsewhere. Costs associated with this treatment may be billed to the participant's insurance company. Costs not covered by participant's insurance company will be the participant's responsibility.
- The study has been approved by the UCF Health Privacy Officer.

7) Study Design

a) Recruitment Methods

- For this study, we will recruit 25 adult male and female volunteers age 18 years and older. This number was calculated with the University of California San Francisco (UCSF) Clinical and Translational Science Institute Sample Size Calculator with a power of 0.8, effect size of 0.25, and alpha of 0.05.

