- Participants with a diagnosis of cutaneous lupus will be recruited from the UCF Health Clinic during a patient's visit (medical records will not be searched for patients with a diagnosis of cutaneous lupus) and through advertising on the UCF Health website and within the UCF Health clinic. Potential participants also will be identified through email by the Lupus Foundation of Florida to its membership and the Central Florida Society for Dermatology. (See attached "Advertisement").
- [name] and [name] will rely on prior labs, pathology reports, and physical examination to determine if the participant has cutaneous lupus.
- If interested in participating, participants will contact the primary or co-investigator, who will provide instructions on how to enroll in the study.
- The investigator will describe the details of the study and answer any questions the participant may have about the study. Participants will be given an informed consent about the study and the primary investigator's contact information. Those participants who express interest in the study will be required to sign the HIPAA Authorization form (attached), Informed Consent form (attached) to ensure that there is no coercion in the study. Each of these will be signed both by the participant and by [name].

b) Participant Compensation

- The study participants will not be receiving any compensation for their participation in the study.

c) Inclusion and Exclusion Criteria

- For this study, we will recruit approximately 25 male and female volunteers ages 18 and older. All volunteers will be asked to give informed consent and sign a

HIPAA authorization before participation in the experiment. Participants will be screened in person before the research takes place. Participants will be screened and evaluated in the clinic to verify diagnosis through history, physical findings, health records, and previous labs. Participants who fit the diagnosis of cutaneous lupus will be asked whether they wish to participate in the study during the patient visit.

- Inclusion Criteria:
 - Male or female adult 18 years of age or older
 - Ability to rate level of pain
 - Ability to rate visual satisfaction
 - At least 2 active lesions of CLE

- Exclusion Criteria:
 - New or change in systemic medication for cutaneous lupus in past 6 months
 - Allergy to triamcinolone or betamethasone dipropionate cream
 - Pregnancy
 - Currently a prisoner

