 - Unable to read and speak English since consent will only be available in English

[figure not shown]
- d) Study Endpoints
 - Primary endpoints: Participation in the study will end after the third visit.
 - Primary safety endpoints: none
 - Secondary safety endpoints:
 - Adverse reaction to the laser treatment such as blister, ulceration, and scarring.
 - Adverse reaction to the topical steroid such as atrophy, telangiectasias or striae.
 - Intolerance to pain of laser procedure.

- e) Study Timelines
 - Each participant will be in the study for a maximum of 8 weeks. Participants will receive 2 laser treatments. The laser treatments will be spaced 4 weeks apart between visit 1 and visit 2. Finally, 4 weeks after visit 2, the participants will be followed up during visit 3.

 - The duration expected for all study participants to be recruited is estimated to be 28 weeks.

 - The study will end when the last participant has completed the 2 laser treatments and follow up. The goal is to conclude the data collection by October 31, 2018 and complete primary analysis by December 31, 2018.

- f) Procedures involved in the Human Research.
- This study will be a randomized prospective study. All study lesions will receive topical treatment. One lesion will only receive topical treatment to serve as a control, and up to 2 others will also receive laser treatment in addition to the topical treatment.
 - Standard of care treatment will be a topical corticosteroid as follows:
 - Discoid lupus lesions: Betamethasone dipropionate augmented 0.05% cream twice a day as needed
 - Non-discoid cutaneous lupus lesions: Triamcinolone acetonide 0.1% cream twice a day as needed
 - Laser treatment will be randomized based upon the participant Fitzpatrick Skin Type as follows:
 - Fitzpatrick Skin Types I – III:
 - § Treatment lesion will be treated with 532nm laser or 1064nm laser
 - § 50:50 randomization for laser used (determined by coin flip)
 - § If the participants have an additional lesion then this will be treated with the laser not used for the treatment lesion
 - Fitzpatrick Skin Types IV - VI
 - § Treatment lesion will only be treated with the 1064nm laser. This is because the 532 nm wavelength is absorbed easily by melanin and thus can cause skin pigmentation abnormalities when used with darker skin participants.
 - Laser treatment system details and parameters:

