 - The Excel V laser system manufactured by Cutera (Brisbane, CA) will be used to administer all laser treatments. This laser has the capability of emitting both 532nm and 1064nm wavelengths.
 - Treatments with the 532nm wavelength will utilize parameters in the following ranges:
 - § Spot size: 1-12mm
 - § Fluence: 5-12 J/cm²
 - § Pulse Duration: 3-15ms
 - § Temperature: 5-10°C
 - Treatments with the 1064nm wavelength will utilize parameters in the following ranges:
 - § Spot size: 1-12mm
 - § Fluence: 10-60 J/cm²
 - § Pulse Duration: 10-60ms
 - § Temperature: 5-10°C
 - Note: If the lesions are ill-defined such as those of ACLE and SCLE then a lesion will be defined as a 2cm² within the involved area.

- Timeline:

Pre-Week 0: Screening Visit

- Screening: participant will be screened for inclusion and exclusion criteria, including urine pregnancy test if necessary.

Week 0: Visit 1

- Baseline lesion assessment, lesion selection, randomization and treatment 1 will occur.

Week 4: Visit 2

- Follow up lesion assessment
- Treatment 2

Week 8: Visit 3

- Final lesion assessment

- Lesion assessment:

Limited CLASI:

The classification of cutaneous lupus will be recorded for each participant.

A “limited” CLASI scoring system will be used, subdivided into an “active” and “damage” components.

The limited active CLASI for a lesion will include the following:

- Erythema (ranging from 0 = absent to 3 = dark red/purple)
- Scale/Hypertrophy (ranging from 0 = absent to 2 = verrucous/ hypertrophic)
- The addition of these scores result in a total limited active CLASI score of the studied lesion, ranging from 0 to 5.

The limited damage CLASI for a lesion will include the following:

- Dyspigmentation (0 = absent or 1 = present)
- Scarring/Atrophy/Panniculitis (ranging from 0 = absent to 2 = severely atrophic scarring or panniculitis).
- The addition of these scores result in a maximum damage score of 3.

The total limited CLASI reflects the sum of both active and damage CLASI, resulting in a score ranging from 0 to 8.

Photographs will be taken of all study lesions during every assessment.

All participants will be evaluated by [name] at baseline and at subsequent visits.

All participants will be evaluated via photograph by [name] at baseline and subsequent visits. [name] will be blinded to the treatment type so as to be an independent observer. He will utilize the “Independent Observer Survey” to document his assessments.

Visual Satisfaction of Appearance:

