g) Data and specimen management

There will be no specimen collection, and thus there will be no management of physical specimens.

If a participant withdraws from the study, the reason for the withdrawal will be noted but data collected up to that point will be used.

All data will be collected on the survey documents (see attached documents “Survey” and “Independent Observer Survey”). These survey documents will be stored in regulatory binder in a locked drawer in locked room at UCF Health. This will only be accessible only to the principal investigator and co-principal investigators. These survey documents will then be used to transfer the data to the REDCap database, afterwards they will be disposed of in HIPAA-compliant shred bin.

Photographs of study lesions will be stored directly in the EHR.

The data will be analyzed for significant differences with aid of a statistician. A significance level of 0.05 will be used for statistical hypothesis testing. The results of the data analysis will be graphed for each parameter.

h) Provisions to monitor the data for the safety of participants

The principal investigator and statistician will periodically review cumulative CLASI scores and adverse effect data every 10 patients.

If the change in the active CLASI score for the treatment lesion is 3 points higher than the change in the active CLASI score for control lesions with $p < 0.05$ then the study will be suspended immediately.

If participants have ulceration or scarring attributable to the laser treatment as an adverse effect with $p < 0.05$ then the study will be suspended immediately.

i) Withdrawal of participants

Participants will be withdrawn from the research without their consent if they become intolerant to the laser treatments and/or the investigators determine that they are too nervous, anxious to continue.

Participants may terminate their participation in the research study at any time by informing a member of the research team. If the participant declines any further laser treatments he or she may still participate in the study with follow up assessments being completed.

If participants miss study Visit 2, the researchers will attempt to reach the participant to reschedule. If the participant is unable to reschedule within 2 weeks of the missed appointment then the participant will forego the 2nd treatment and attempted to be scheduled for Visit 3.

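### The 25 participants do not follow from the stated power 0.8, effect size 0.25 and alpha 0.05 on the natural paired reading, and no section gives the metric or variance input that would support them

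*Combined protocol and SAP*

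**What the plan says.** Section 7a (Recruitment Methods) gives the only justification for the sample size: 25 adults, calculated with a "Sample Size Calculator with a power of 0.8, effect size of 0.25, and alpha of 0.05".

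The rest of the protocol fills in part of the picture:

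- **Comparison.** Section 3 (Objectives) compares each laser plus topical steroid with topical steroid alone. It hypothesises quicker resolution with laser, and that 532nm is more effective than 1064nm.
- **Design.** The comparison is within participant. Section 7c requires "At least 2 active lesions of CLE", and section 7f says "One lesion will only receive topical treatment to serve as a control, and up to 2 others will also receive laser treatment".
- **Endpoint.** The entry in section 7d reads "Primary endpoints: Participation in the study will end after the third visit", which names no efficacy variable.
- **Analysis.** Section 7g says "A significance level of 0.05 will be used for statistical hypothesis testing" and leaves the choice of test to a statistician.
- **Outcome scale.** Section 7f defines a "total limited active CLASI score of the studied lesion, ranging from 0 to 5". Section 7h compares this score between lesions ("If the change in the active CLASI score for the treatment lesion is 3 points higher than the change"), but only as a suspension rule. It gives no SD, and section 7a does not refer to it.

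**The concern.** An effect size of 0.25 has no meaning for sample size until its metric is known, and for most metrics an SD, a correlation or a rate is needed as well. None is stated. In a design where every participant supplies a laser lesion and a control lesion, the natural reading is a standardised paired difference. On that reading the three inputs lead to a number about five times larger than 25 (128/25 = 5.1).

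Section 4 says that the study hopes to quantify the size of the effect, and section 3 states superiority hypotheses. A reader who takes 80% power for 0.25 at face value cannot tell what the trial is able to detect, and so cannot interpret a non-significant result against the design.

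**Working it through.** **Inputs.** N = 25, power 0.80, effect 0.25 and alpha 0.05 come from section 7a (0.05 again in 7g). Pairing comes from 7c and 7f. Sidedness is not stated, so both are shown. Every SD, correlation or rate below is an assumption, because the documents give none.

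**1. Attempt to reproduce 25.** For a paired t-test with standardised difference d = 0.25, the normal approximation is n = ((z_alpha + z_beta)/d)².

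- Two-sided: ((1.960 + 0.842)/0.25)² = 125.6, so 126. Noncentral t gives 128.
- One-sided: ((1.645 + 0.842)/0.25)² = 99.0, so 99. Noncentral t gives 101.

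Other standardised readings that add no further value, two-sided: 253 per arm for two independent groups, 124 for a correlation of 0.25, and a total of 128 or 158 for a one-way ANOVA with f = 0.25 and two or three groups. None is near 25.

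**2. Power with 25 on the paired reading.** Noncentrality is 0.25 × √25 = 1.25 on 24 degrees of freedom. Power is 22% two-sided and 33% one-sided.

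**3. Readings that do reach about 25.**

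| Reading of 0.25 | Unstated item | Result (two-sided unless noted) |
|---|---|---|
| Raw points, noncentral t | SD of the paired difference | 80% with 25 at SD 0.25/0.584 = 0.43 (one-sided 0.25/0.512 = 0.49). Power 67% at SD 0.5, 36% at 0.75, 22% at 1.0 |
| Raw points, exact on differences of 0 or ±1 | Shares better and worse | 26.25% better, 1.25% worse: SD = √(0.275 − 0.0625) = 0.46, power 79% |
| Fraction of the between-lesion SD, d = 0.25/√(2(1 − ρ)) | Correlation ρ | 80% at ρ about 0.91; 48% at 0.8, 22% at 0.5 |
| Cohen's f, λ = f²·n·m/(1 − ρ) | Correlation ρ | 80% at ρ about 0.63 (m = 2 conditions) or 0.54 (m = 3) |
| One-sample proportion, 0.25 against 0.50 | Null rate | ((1.960√(0.25 × 0.75) + 0.842√(0.5 × 0.5))/0.25)² = 25.8, so 26 |
| Paired proportions (McNemar), difference 0.25 | Discordance | 29 at discordance 0.25, 36 at 0.30; one-sided 23 and 28 |
| Partial eta-squared, two lesions | The metric only | d = √(0.25/0.75) = 0.577; power 79% with 25, n = 26 |

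**4. What 25 pairs deliver.** For a paired t-test on a roughly continuous outcome, the difference detectable with 80% power is 0.58 SD of the paired difference (0.51 one-sided). The 95% confidence interval half-width is t(0.975, 24)/√25 = 2.064/5 = 0.41 SD. In points, under assumed SDs of 0.5, 0.75 and 1.0, the detectable difference is 0.584 × SD = 0.29, 0.44 and 0.58.

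**The case against.** The strongest reply is that this is incomplete reporting, not a demonstrated error. Section 7a names a specific calculator whose prompts cannot be seen. Several ordinary entries give 25 or 26, and one of them, partial eta-squared 0.25, needs no variance input at all. Nothing says that 0.25 was meant as a standardised paired difference. All of this stands. A reader might infer that the trial needs 128 participants, or that its power is 22%; the documents support neither, because both figures hold only on that one reading.

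Three further inferences also fail:

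- **That the raw-points reading is impossible on a whole-point score.** With whole-point differences averaging 0.25, the SD cannot be below √(0.25 × 0.75) = 0.433. At that floor, however, the exact power of the two-sided paired t-test is 90%, because it rejects when 4 or more of 25 participants improve. The floor does not exclude the reading.
- **That power lies between 22% and 80%.** These are not bounds. The between-lesion SD reading gives 14% at correlation 0, and one-sided partial eta-squared gives 88%.
- **That a null result could not rule out 0.25 SD.** It could if the estimate were below about 0.25 − 0.41 = −0.16 SD. Only estimates above that leave 0.25 SD open.

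What the reply does not remove is that the protocol makes a definite power claim, does not present 25 as a feasibility number, and gives no section from which the claim can be checked.

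**Conclusion.** The concern holds as a statement about support. The three stated inputs do not give 25 on the natural paired reading: power is 22% two-sided (33% one-sided), and 80% needs 128 (101 one-sided). Each route to about 25 depends on a metric that is not stated and, except for partial eta-squared, on an SD, correlation or rate that is not stated either. The stated 80% power for 0.25 is therefore unsupported as written, while 25 itself is not disproved.

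The 22% and 128 assume a paired t-test on a roughly continuous outcome, with 0.25 in units of the SD of the paired difference. The calculation also leaves the second hypothesis in section 3 uncovered. For skin types IV to VI, section 7f says "Treatment lesion will only be treated with the 1064nm laser", so only types I to III can inform 532nm against 1064nm. The point should be fixed, but it does not call for a different sample size.

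**What to change.** Keep N = 25. Replace the power sentence in section 7a with what the design delivers for a named outcome and test, for example:

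> With 25 participants, a two-sided paired t-test (alpha 0.05) of the week 8 change in limited active CLASI, treatment lesion versus control lesion, has 80% power for a mean difference of 0.58 SD of the paired difference; the 95% confidence interval extends about 0.41 SD either side.

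The sponsor should:

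- confirm the outcome. Limited active CLASI is offered because section 7h already compares it between lesions; section 3 speaks of quicker resolution, so a week 8 change is a choice to be made openly;
- give the detectable difference in CLASI points under a stated SD or range of SDs;
- note that the t-test figure is approximate for a whole-point score from 0 to 5;
- use 0.51 SD if a one-sided test is specified;
- keep 80% power for 0.25 only if the metric, and any SD, correlation or rate behind it, is stated;
- say that the calculation does not cover 532nm against 1064nm, and report that comparison as an estimate with a confidence interval.

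The cost is one paragraph and one named outcome, with no extra participants, visits or procedures. The downside is a less favourable stated figure, unless the missing input can be supplied.

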CLE is typically categorized as acute (ACLE), subacute CLE (SCLE), and chronic (CCLE). ACLE develops in nearly one half of patients with SLE, but most or all people with ACLE have SLE. Also known as "malar rash" or "butterfly rash", ACLE is characterized by erythema distributed over the cheeks and nasal bridge of the face.¹ SCLE is less common but may appear as round, scaly lesions with central clearing. Discoid Lupus Erythematosus (DLE), a form of CCLE, is one of the most common forms of cutaneous lupus and can appear as erythematous and hyper- and hypopigmented lesions with telangiectasias. Frequently these lesions lead to scarring and can be permanently disfiguring.

First line management of CLE involves photo protection along with topical corticosteroids and possibly systemic agents. Other treatments include intralesional steroids and/or topical calcineurin inhibitors.¹ Both topical and systemic medications carry a wide range of adverse and toxic effects.³⁻⁵

Though not well-known, laser therapy has been shown to be effective in the treatment of cutaneous lupus.⁶⁻⁸ Many providers may be wary of using lasers on these patients given the ability of ultraviolet light to exacerbate or flare SLE.^{9,10} It is believed that by targeting the superficial vasculature the lasers are able to attenuate the inflammatory response seen in the skin.¹¹

The 585 nm, 595 nm and 1064 nm wavelength lasers have all been shown to be effective in the treatments of cutaneous lupus.^{6-8,12} Given their ability to target vasculature, these lasers are currently used to treat vascular lesions and inflammatory conditions such as port wine stains, telangiectasias, hemangiomas, rosacea, and scars.^{13,14}

Lasers utilizing the 532nm wavelength also have been shown to treat the same vascular and inflammatory conditions as the above mentioned wavelengths. This is due to the fact that the 532nm laser targets the same chromophore of oxyhemoglobin.^{15,16}

Therefore, given that the 532nm has very similar properties and same mechanism of action as other vascular lasers shown to be effective at treating cutaneous lupus it would be reasonable to consider that the 532nm laser could be utilized to treat cutaneous lupus as well.¹⁷

However, since the 532 nm should be used with caution in darker skin people and SLE is 2 to 4 times higher in African-American women than Caucasian women, utilizing only the 532nm would limit the applicability of the proposed study.^{14,18}

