Therefore, we are proposing investigating the use a 1064nm laser as well in treating cutaneous lupus as this wavelength is safe on people of all skin types.⁹ The 1064nm laser has previously been shown to be effective in cutaneous lupus though further studies are needed to confirm the preliminary findings and better characterize the effectiveness.¹¹

When compared to available topical and systemic therapies, laser therapy generally has been shown to have minimal side effects. The most common adverse effect is bruising

but that usually clears within 10 days. Other adverse effects include temporary dyspigmentation and very rarely scarring, vesiculation, and crusting that usually fade within a few weeks.¹⁴

The 532nm laser and 1064nm wavelength lasers are currently being used in an off-label manner by [name] of UCF Health to treat patients with cutaneous lupus with excellent clinical results. As there is limited data on the use of the 532nm and 1064nm lasers for cutaneous lupus, we hope to quantify the magnitude of the results in a prospective manner.

As lasers with these wavelengths are present in many dermatology practices, we hope that data from this study will educate and encourage more providers to use lasers, such as the one in this study, to benefit their patients with cutaneous lupus.

5) Setting of the Human Research

- The human research will be conducted at UCF Health Clinic at [name].
- UCF College of Medicine's resources will be used during data analysis
- We have obtained permission and approval from UCF Health medical director [name]

6) Resources available to conduct the Human Research

- Participants will be recruited through the UCF Health Clinic, Lupus Foundation of Florida, and the Central Florida Society of Dermatology. This represents a large pool of potential participants from which to recruit.
- The study's small sample size (N=25) makes it likely that the required number of participants will be recruited in less than 12 months.

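### Prior local treatment of study lesions is neither restricted nor clearly recorded, and the control lesion is not stated to be random, so the laser-versus-control contrast can be biased

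*Combined protocol and SAP*

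**What the plan says.** The exclusion list in Section 7(c) has one item on earlier treatment: "New or change in systemic medication for cutaneous lupus in past 6 months". The other items are pregnancy, being a prisoner, "Allergy to triamcinolone or betamethasone dipropionate cream" and "Unable to read and speak English since consent will only be available in English". The only lesion-level inclusion criterion is "At least 2 active lesions of CLE".

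Section 7(f) makes the comparison within a participant: one lesion has topical steroid alone, and up to two others have laser as well. For skin types I to III a coin flip decides which laser the treatment lesion receives. For types IV to VI the laser is always 1064 nm. Lesions are selected at Visit 1, with no stated selection rule.

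On earlier exposure, Section 4 notes "Other treatments include intralesional steroids and/or topical calcineurin inhibitors" and says "The 532nm laser and 1064nm wavelength lasers are currently being used in an off-label manner" at UCF Health for cutaneous lupus. Section 6 lists 532 nm laser for cutaneous lupus among the off-label treatments given there. Under Section 7(a), participants "will be recruited from the UCF Health Clinic during a patient's visit", as well as through advertising, a lupus foundation and a dermatology society.

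**The concern.** A within-participant design removes whatever the lesions share, and a systemic drug is shared. A laser session, a steroid injection or a cream can be given to one lesion and not to another, and those differences do not cancel. The plan therefore controls the exposure that matters less to its main contrast and leaves open the one that matters more.

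Followed exactly, the plan would accept a participant whose lesion was lasered shortly before enrolment and would allow that lesion to be the topical-only control. It would equally accept a recently injected lesion as the laser lesion. In both cases part of the measured difference would come from treatment before the trial. The same contrast feeds the suspension rule in Section 7(h), which compares the change in active score between treatment and control lesions.

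**Working it through.** The plan states no figure on this point, so there is none to reproduce. The check is a comparison of the text, followed by an illustration under stated assumptions.

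**1. Is prior local treatment controlled anywhere?** The exclusions in 7(c) do not mention it. Activity of the lesion is required, but nothing is said about what was done to it before. The data list in 7(f) includes medications and medical history, which are not specified by lesion, and an undefined item on lesion treatment that may mean only the assigned treatment. The Survey form is not part of the available text, so the finding is only that the protocol does not clearly specify the item.

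**2. Does allocation protect the contrast?** The flip chooses between two lasers. It does not choose between laser and control, and it does not exist for skin types IV to VI. No other allocation mechanism is described, so prior treatment is not balanced by design between the control and laser lesions.

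**3. Is carry-over plausible on the plan's own timescale?** Visit 3 is 4 weeks after the second laser session. Section 7(i) lets a missed Visit 3 be rescheduled within 6 weeks, so an effect is still assessed up to 4 + 6 = 10 weeks after laser. A lesion lasered a month before Visit 1 is inside that window at baseline.

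**4. Size.** Let q be the net imbalance, (participants with only the control lesion pretreated − participants with only the laser lesion pretreated) / 25, taken in absolute value. Let c be the carry-over in points on the 0 to 5 limited active CLASI. Then

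bias = q × c.

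The share of participants with any pretreated lesion does not fix q. If 10 of 25 have one pretreated lesion, split evenly, q = (5 − 5)/25 = 0 and so is the bias.

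The documents give neither q nor c. Assumed ranges: q from 0 to 0.3 and c up to 1 point. The bias then runs from 0 to 0.3 × 1 = 0.3 points.

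**5. Effect on the test.** This assumes 25 complete pairs, a two-sided paired t test at 0.05 (the plan states 0.05 but not the sidedness), no true laser effect, and a paired-difference SD of 1.0 or 1.5 (the documents give none). The rejection rate comes from the noncentral t distribution with 24 degrees of freedom and noncentrality (bias / SD) × √25.

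| Bias (points) | Example q × c | Rejection rate, SD 1.0 | Rejection rate, SD 1.5 |
|---|---|---|---|
| 0 | 0 × 1.0 | 5.0% | 5.0% |
| 0.05 | 0.1 × 0.5 | 5.7% | 5.3% |
| 0.10 | 0.1 × 1.0 | 7.7% | 6.2% |
| 0.15 | 0.3 × 0.5 | 11.1% | 7.7% |
| 0.20 | 0.2 × 1.0 | 16.1% | 9.8% |
| 0.30 | 0.3 × 1.0 | 30.2% | 16.1% |

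**6. Direction.** Section 7(h) works with change from the Visit 1 baseline. Suppose the control lesion was lasered earlier. If that effect is still developing after baseline, the control improves more and the laser benefit is understated. If it is already complete, the control starts lower with less room to improve, and the benefit is overstated. The reverse holds for a pretreated laser lesion. The direction cannot be fixed in advance.

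**The case against.** The best defence is that the documents do not show that any study lesion will have been pretreated, still less unequally. Lesions must be active, each is scored at baseline, and medications, history and photographs are available from the health record. Recruitment also runs outside the clinic, and the off-label list in Section 6 names only 532 nm for cutaneous lupus, though that list is not exhaustive. All of this stands, and it is why the conclusion is that bias can arise, not that it will. These safeguards are partial: an active lesion with a baseline score can still carry an effect that develops afterwards.

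Four stronger readings are tempting and are not supported:

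- A reader might take the 6-month criterion for a washout. It excludes new or changed systemic drugs, and unchanged ones may continue. It gives no basis for a 6-month interval free of local treatment.
- A reader might infer that a pretreated control lesion always hides a laser benefit, and that a pretreated laser lesion always inflates it. With a change score either can go the other way.
- A reader might infer that the clinic's returning patients are known laser responders. Section 4 reports a general impression of good results, and the requirement for active lesions could equally select patients who responded incompletely or relapsed.
- A reader might infer that the bias could never be corrected afterwards. The Survey form is not in the text and the health record is available, so this is not established.

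**Conclusion.** The point holds as a gap in eligibility, recording and allocation at the lesion level. Unequal prior local treatment can bias the laser-versus-control contrast in either direction, and nothing in the plan prevents it. The size is unknown and may be zero. Under the assumed imbalance (0 to 0.3) and carry-over (up to 1 point), the bias is 0 to 0.3 points on the active score. With the assumed SDs, the false-positive rate is between its nominal 5% and 30.2%. These figures show sensitivity and are not estimates for this trial. Confidence is high that the gap exists; the documents cannot say how much it matters. The plan should be changed on this point because the remedy is cheap and prior exposure is easiest to capture at Visit 1.

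**What to change.** 1. In Section 7(c), add an eligibility condition on recent local treatment of any study lesion, control or laser, covering laser, intralesional steroid, calcineurin inhibitor and other local treatment. The investigators should set and state the interval. Apply the condition to the lesion, so that a participant with enough other active lesions stays eligible.
2. At Visit 1, record each study lesion's prior local treatment and its date on the Survey.
3. In Section 7(f), select the lesions first, then randomize which of them is the control, for all skin types. This balances prior treatment in expectation only. With 10 participants who have one pretreated lesion, the standard deviation of the signed net imbalance is √10 / 25 = 0.13, so steps 1 and 2 are still needed.
4. In Section 7(g), specify a sensitivity analysis that leaves out pairs with unequal prior local treatment.

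The cost is one criterion, one Survey line, one allocation step and one secondary analysis in an amendment. A few existing laser patients of the clinic may lack two qualifying lesions, and the sensitivity analysis will use fewer than 25 pairs if any are unequal.
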